### **5.3.3 Hematologic Toxicity**

Grade 1, 2 and 3 myelosuppression (neutropenia, thrombocytopenia), with recovery to pre-treatment lab criteria as specified in the inclusion criteria, does not require dose modification. Grade 3 or 4 lymphopenia does not require dose reduction. Patients with a febrile Grade 4 neutropenia >7 days or Grade 4 neutropenia associated with fever (one reading of oral temperature > 38.5° C, or three readings of oral temperature > 38.0° C in a 24-hour period) or Grade 4 thrombocytopenia >7 days should be retreated after recovery at a one-dose level reduction during subsequent cycles. If any of these toxicities recurs, the patient should be dose reduced again in all subsequent cycles after recovery to pre-treatment lab criteria as specified in the inclusion criteria. Patients will not be eligible for further treatment if resolution of toxicities requires a greater than 2-week delay in the start of the next cycle. Patients who need two dose level reductions of TAS-102 will discontinue from the study.

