### 5.3 Dose Modifications

The National Cancer Institute (NCI) Common Toxicity Criteria for Adverse Events Version 4 (CTCAE) will be used to grade toxicity (<http://evs.nci.nih.gov/ftp1/CTCAE/About.html>).

The starting dose of TAS-102 is 35 mg/m^2 up to a maximum of 80 mg per dose (based on the trifluridine component) orally twice daily within one hour of completion of morning and evening meals on Days 1 through 5 and Days 8 through 12 of each 28-day cycle until disease progression or unacceptable toxicity. Doses will be rounded to the nearest 5 mg increment. Study medication will be administered on a 4 week schedule. Doses will be delayed or reduced for clinically significant (Grade 3-4) hematologic and non-hematologic toxicities that are related to protocol therapy according to the guidelines shown in the Dose Delays/Dose Modifications table that follows. Dose modifications will follow predefined dose levels. Dose adjustments for hematologic toxicity are based on the blood counts obtained in preparation for the day of treatment.

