#### 5.3.1 Dose Modification Table

Dose level 0 (standard starting dose)	35 mg/m  po bid
Dose level – 1	30 mg/m  po bid
Dose level – 2	25 mg/m  po bid

Inpatient dose reduction and dose interruption will be permitted once a patient has experienced drug-related toxicity provided that the criteria for patient withdrawal from study treatment have not been met. All inpatient dose reductions are relative to the lowest dose of the current cycle.

For all toxicities, doses of TAS-102 will be modified based upon Day 1 and Day 15, complete blood cell counts. Day 1 TAS-102 dosing for each cycle will be held until:

- Absolute neutrophil count (ANC) is greater than or equal to 1,500/mm^3 or febrile neutropenia is resolved

- Platelets are greater than or equal to 75,000/mm^3
- Grade 3 or 4 non-hematological adverse reactions are resolved to Grade 0 or 1

Within a treatment cycle, TAS-102 will be withheld for any of the following:

- Absolute neutrophil count (ANC) less than 500/mm^3 or febrile neutropenia
- Platelets less than 50,000/mm^3
- Grade 3 or 4 non-hematological adverse reactions

After recovery, resume TAS-102 after reducing the dose by 5 mg/m^2/dose (as above) from the previous dose level, if the following occur:

- Febrile neutropenia
- Uncomplicated Grade 4 neutropenia (which has recovered to greater than or equal to 1,500/mm^3, or baseline in subjects with benign ethnic neutropenia) or thrombocytopenia (which has recovered to greater than or equal to 75,000/mm^3) that results in more than 1-week delay in start of next cycle
- Non-hematologic Grade 3 or Grade 4 adverse reaction except for Grade 3 nausea and/or vomiting controlled by antiemetic therapy or Grade 3 diarrhea responsive to antidiarrheal medication

If a subject experiences more than one toxicity, dose reduction should be according to the toxicity with the highest grade. In the case of two or more toxicities of the same grade, the investigator may dose reduce according to that deemed most causally related to study treatment. If more than 3 dose reductions are required, TAS-102 will be discontinued. Do not escalate dose after it has been reduced.

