### **5.3.2 Non- Hematologic Toxicity**

For Grade 3 and 4 toxicities, treatment should be withheld until the toxicity resolves to Grade 1 or less (or to baseline), then reinstated (if medically appropriate) at a one level dose reduction. Nausea and vomiting or diarrhea must persist at Grade 3 or 4 despite maximal medical therapy. All agents should be dose reduced in cases where either agent may be the cause of a given toxicity. Patients must meet pre-treatment laboratory criteria (as specified in the inclusion criteria) at Day 1 of each cycle to receive therapy administration. Patients will not be eligible for further treatment if resolution of toxicities requires a greater than 3-week delay in the start of the next cycle (five weeks from the start of the prior cycle).

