### 6.4 **Study Discontinuation**

It is unlikely that the trial itself will require a premature termination. However the trial will be stopped prematurely (prior to completion of accrual, protocol therapy, and follow-up) for safety reasons if the therapy at Dose level 0 is intolerable in the first six patients, requiring dose reduction to Dose level -1.

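### Sections 5.3.1 and 5.3.3 give different haematologic dose-reduction triggers and different Day 1 recovery limits, and the protocol does not say which governs

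*Combined protocol and SAP*

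**What the plan says.** Section 5.3 handles Grade 3-4 related toxicity "according to the guidelines shown in the Dose Delays/Dose Modifications table that follows". The only table that follows is in 5.3.1. It lists three dose levels (35, 30 and 25 mg/m²), with the triggers in text and bullets beneath it.

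**Triggers.** Section 5.3.1 opens broadly: "For all toxicities, doses of TAS-102 will be modified based upon Day 1 and Day 15, complete blood cell counts". After recovery it takes the dose down by 5 mg/m² for febrile neutropenia, with no grade or duration condition. It does the same for uncomplicated Grade 4 neutropenia or thrombocytopenia "that results in more than 1-week delay in start of next cycle".

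Section 5.3.3, headed for haematologic toxicity, first says that Grade 1 to 3 myelosuppression that has recovered to the inclusion limits needs no modification. It then reduces for Grade 4 neutropenia with fever (temperature limits given) and for what is printed as *a febrile* Grade 4 neutropenia of more than 7 days. For platelets it says "Grade 4 thrombocytopenia >7 days should be retreated after recovery at a one-dose level reduction during subsequent cycles". Treatment ends if recovery "requires a greater than 2-week delay in the start of the next cycle".

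**Day 1 limits.** Section 5.3.1 states "Day 1 TAS-102 dosing for each cycle will be held until" ANC is at least 1,500 and platelets at least 75,000; the ANC line also offers resolution of febrile neutropenia as an alternative. Section 5.3.2 states "Patients must meet pre-treatment laboratory criteria (as specified in the inclusion criteria) at Day 1 of each cycle to receive therapy administration". Those limits, in section 3.2 item H, are ANC 1,000 and platelets 100,000, and 5.3.3 uses them as its recovery point. Section 11.4 separately asks for documented return to baseline before later courses.

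**The concern.** One section counts how late the next cycle starts; the other counts days at Grade 4. The same event can therefore appear in one list and not in the other. The two sections also disagree on the counts at which a patient may restart, and that decides whether a cycle is late at all.

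The stake is consistent dosing of a drug that section 9.1.7 describes as causing severe and life-threatening myelosuppression. Two sites, each following a written section, could treat like patients differently. The by-dose-level safety summaries in 11.4 would then partly reflect which section was followed. A reduction is also permanent, because 5.3.1 forbids re-escalation.

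**Working it through.** No sample size, power or error rate is involved. The check sets the two sets of rules side by side.

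**Step 1: triggers as yes/no rules.** I read Grade 4 and the delay condition in 5.3.1 as applying to both cell lines.

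- 5.3.1: reduce if (neutropenia with fever) or (Grade 4 with next cycle more than 1 week late).
- 5.3.3: reduce if (Grade 4 neutropenia with fever) or (Grade 4 thrombocytopenia lasting more than 7 days). If *a febrile* was meant as *afebrile*, add (Grade 4 neutropenia lasting more than 7 days).

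The combinations of cell line, Grade 3 or 4, fever (neutropenia only), Grade 4 for more than 7 days, and delay of more than 1 week number 4 + 8 for neutropenia and 2 + 4 for thrombocytopenia, 18 in all. The rules differ in these:

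| Event | 5.3.1 | 5.3.3 | Reading of *a febrile* |
|---|---|---|---|
| Neutropenia, Grade 3 count, fever, no delay >1 week | reduce | no modification required once recovered | both |
| Same, with delay >1 week | reduce | no modification required once recovered | both |
| Grade 4 neutropenia, no fever, ≤7 days, delay >1 week | reduce | not listed | both |
| Grade 4 thrombocytopenia, ≤7 days, delay >1 week | reduce | not listed | both |
| Grade 4 thrombocytopenia, >7 days, no delay >1 week | not listed | reduce | both |
| Grade 4 neutropenia, no fever, >7 days, delay >1 week | reduce | not listed | as printed |
| Grade 4 neutropenia, no fever, >7 days, no delay >1 week | not listed | reduce | as *afebrile* |

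Five rows hold under both readings and one more under each, so the rules differ in 6 of 18 combinations either way. This counts rule combinations, not patients. As printed, the *a febrile* clause adds nothing to the clause on Grade 4 neutropenia with fever, which suggests that *afebrile* was intended.

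**Step 2: which differences can be reconciled.** Where one section reduces and the other is silent, reducing on either trigger satisfies both. That covers every row except the first two. There 5.3.3 is not silent: it says that a recovered Grade 3 count does not require modification, while 5.3.1 reduces for any febrile neutropenia.

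**Step 3: Day 1 limits.**

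| Day 1 count | 5.3.1 | Inclusion limits (5.3.2, 5.3.3) |
|---|---|---|
| ANC 1,000 to 1,499 | hold | met |
| Platelets 75,000 to 99,999 | met | not met |

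Neither standard is uniformly the stricter.

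**Step 4: the limits feed the delay trigger.** Section 5.3.1 needs a delay of more than 7 days, and 5.3.3 ends treatment beyond 14 days. Under both, the delay trigger can act only at 8 to 14 days. Suppose a patient's ANC passes 1,000 in the first week of delay but reaches 1,500 only in the second. The start is late enough to trigger a reduction under 5.3.1's limit, but not under the inclusion limit.

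**Step 5: dose at stake.** One level is 5/35 = 14.3%. At an assumed body surface area of 1.8 m², 35 × 1.8 = 63 rounds to 65 mg and 30 × 1.8 = 54 rounds to 55 mg. That is 10 mg per dose, or 200 mg over the 20 doses of a cycle. Over an assumed 1.4 to 2.4 m², with 5 mg rounding and the 80 mg cap, the difference is 5 to 15 mg per dose.

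**The case against.** The strongest reply is that nothing here conflicts. Both trigger lists are sufficient conditions; neither says *only if*. A site must follow the whole protocol, so it reduces when either list applies. The Day 1 limits are likewise joint requirements, all met at ANC 1,500 and platelets 100,000. Wording that modification is not required does not prohibit it. And section 5.3, with 5.3.1's opening words on all toxicities, points to 5.3.1 as the governing section.

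Much of this stands. For the rows where one section is silent, reducing on either trigger complies with both, and a reader who infers outright contradiction in every row goes beyond the text. What remains is that the protocol nowhere tells sites to combine the lists.

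The rest is weaker. Taking the stricter Day 1 limit each time is a choice that the reader has to supply. It would leave 5.3.1's platelet limit of 75,000 and the inclusion ANC limit of 1,000 with no function at Day 1, and 5.3.3 presents the inclusion limits as the recovery point for retreatment. For febrile neutropenia with a Grade 3 count, one section calls for a reduction and the other says that none is needed. The pointer in 5.3 does not settle precedence. The table under it holds only dose levels, and even if 5.3.1's bullets count as part of that table, 5.3.3 still gives its own instruction under the more specific heading. The sentence in 5.3.1 about the highest grade ranks several toxicities in one patient, not two rules for one toxicity.

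**Conclusion.** The point holds as an inconsistency in dosing instructions that should be corrected on patient-safety grounds. Most of the trigger mismatch can be reconciled but is left unstated. Two points pull in opposite directions: restart at ANC 1,000 to 1,499 or platelets 75,000 to 99,999, and febrile neutropenia with a Grade 3 count. The second assumes that febrile neutropenia can be recorded with a Grade 3 count; 5.3.1 sets no ANC limit for it.

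Three stronger conclusions might be inferred, and the documents support none of them.

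- **A count of affected patients.** Section 9.1.7 gives Grade 3-4 rates for the drug (neutropenia 38%, thrombocytopenia 5%). It does not give the Grade 4 share, episode length or frequency of cycle delay, and the rates are not specific to this population. Multiplying them by 30 estimates nothing useful.
- **A changed safety stop.** Section 6.4 stops the trial "if the therapy at Dose level 0 is intolerable in the first six patients, requiring dose reduction to Dose level -1". It turns on intolerability and gives no patient count, so an effect is conceivable but cannot be sized.
- **Damage to the primary analysis.** The sample size and the response-rate estimate use none of these triggers.

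**What to change.** Replace both trigger lists with one list in section 5.3, and state that any one of the following suffices for a one-level reduction:

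- febrile neutropenia of any grade, using 5.3.3's temperature limits;
- Grade 4 neutropenia or thrombocytopenia lasting more than 7 days, correcting *a febrile* if *afebrile* was meant;
- Grade 4 neutropenia or thrombocytopenia that delays the next cycle by more than 1 week.

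Exempt febrile neutropenia from the sentence that recovered Grade 1 to 3 myelosuppression needs no modification. Name one Day 1 ANC and platelet standard, used both for restart and for measuring delay.

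Because an either-trigger rule may slightly increase reductions, settle the discontinuation rule in the same amendment. Section 5.3.3 takes patients off study when two reductions are needed, while 5.3.1 discontinues the drug only when more than three are, although its table has only two lower levels. If the two-reduction rule stays, a few patients could stop earlier.

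The cost is one wording amendment. No extra patients, visits or weekly blood counts are needed.

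### The dose-modification rules conflict: 5.3.3 orders a second reduction and then removes patients who need two, 5.3.1 allows three reductions against two reduced levels, and the 3-week delay in 5.3.2 does not match its five-week gloss

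*Combined protocol and SAP*

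**What the plan says.** All references are to the combined protocol and SAP.

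- **5.3.** TAS-102 is taken twice daily on "Days 1 through 5 and Days 8 through 12 of each 28-day cycle". "Dose modifications will follow predefined dose levels".
- **5.3.1.** The table gives level 0 (35 mg/m² twice daily), level −1 (30) and level −2 (25). One reduction is 5 mg/m² per dose. Reduction is allowed "provided that the criteria for patient withdrawal from study treatment have not been met". The limit is: "If more than 3 dose reductions are required, TAS-102 will be discontinued".
- **5.3.2 (non-hematologic).** Treatment ends if recovery needs a "greater than 3-week delay in the start of the next cycle (five weeks from the start of the prior cycle". This section has no rule that removes a patient after two reductions.
- **5.3.3 (hematologic).** As printed, the events that call for a one-level reduction are febrile Grade 4 neutropenia lasting more than 7 days, Grade 4 neutropenia with fever, and Grade 4 thrombocytopenia lasting more than 7 days. Then: "If any of these toxicities recurs, the patient should be dose reduced again in all subsequent cycles". Treatment ends after a "greater than 2-week delay in the start of the next cycle". The last sentence is: "Patients who need two dose level reductions of TAS-102 will discontinue from the study".
- **6.2.** Treatment also stops for any adverse event that the investigator judges to require it, and after a drug interruption of more than 21 days. The 21-day item points back to the dose-modification section but does not say from which date the days are counted.

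**The concern.** These rules decide, for a cytotoxic drug, who is re-dosed, at what dose, and who comes off treatment. Three of them do not fit together.

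1. Within 5.3.3, a patient whose listed toxicity recurs after a first reduction is ordered both to go down another level and continue, and to leave. Two investigators could act in opposite ways and both cite the same paragraph.
2. The limit of 3 reductions in 5.3.1 counts one more step than the table has.
3. The limit in 5.3.2 is stated twice, with two different lengths. A site that works from the bracketed figure would remove a patient who recovers in the second or third week of delay. A site that works from the main clause would keep that patient.

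There is also a reporting consequence. Section 11.4 plans safety summaries by dose level and fitted dose-toxicity curves. How many patients contribute data at 25 mg/m² depends in part on which sentence of 5.3.3 each site follows.

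**Working it through.** **Step 1. Number of reductions.** Inputs from 5.3 and 5.3.1: start 35 mg/m², step 5 mg/m², table 35, 30, 25. Dose after k reductions = 35 − 5k.

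| k | Dose (mg/m²) | In the table? |
|---|---|---|
| 1 | 30 | yes (level −1) |
| 2 | 25 | yes (level −2) |
| 3 | 20 | no |

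The text therefore gives three maxima: 1 (last sentence of 5.3.3, since needing two means leaving), 2 (the table) and 3 (5.3.1, since only more than 3 means stopping). The third reduction cannot be carried out, because changes must stay on the predefined levels.

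**Step 2. One patient through 5.3.3.** A first listed event takes the patient from 35 to 30 mg/m². The toxicity recurs. The recurrence sentence sends the patient to 25 mg/m² for all later cycles. That is a second reduction, so the last sentence takes the patient off. If the last sentence always wins, the recurrence sentence never operates. If the recurrence sentence wins, the last sentence is not obeyed.

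**Step 3. Dose at stake.** There are 5 + 5 = 10 dosing days at 2 doses a day, so 20 doses per cycle.

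- Level 0: 35 × 20 = 700 mg/m² per cycle
- Level −1: 30 × 20 = 600
- Level −2: 25 × 20 = 500, and 500 / 700 = 71.4%

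For the patient in Step 2 the planned dose is 500 mg/m² per cycle or nothing (before the 80 mg cap and rounding to 5 mg).

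**Step 4. The delay in 5.3.2.** Time from prior cycle start = cycle length + delay.

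- 3-week delay: 28 + 21 = 49 days = seven weeks
- 2-week delay (the 5.3.3 limit): 28 + 14 = 42 days = six weeks
- Five weeks: 35 − 28 = 7 days, a 1-week delay

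The plan's five weeks is not reproduced from its own 3-week limit; the two differ by 49 − 35 = 14 days. Two other counts do give five weeks: a 21-day cycle plus 2 weeks (3 + 2), and 3 weeks from the end of the two-week dosing block (2 + 3). This trial has no 21-day cycle, and the sentence counts delay in the start of the next cycle, so neither fits the words.

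**Step 5. Rough scale.** The adverse-event table in 9.1.9 gives Grade 3 or higher rates on TAS-102 of 3.9% for febrile neutropenia, 1.7% for thrombocytopenia and 2.8% for platelet count decreased. Assume that these rates carry over to 30 patients here.

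- Febrile neutropenia alone: 0.039 × 30 = 1.2 patients
- All three, assuming no overlap: (3.9 + 1.7 + 2.8)% = 8.4%, and 0.084 × 30 = 2.5 patients

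These are first events, and the platelet rates include Grade 3 and short episodes. The conflict needs a recurrence after reduction, for which the documents give no rate.

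**The case against.** The best defence of the reductions text is that the proviso in 5.3.1 makes every reduction subject to the withdrawal criteria. The stop in 5.3.3 would then rank above the limit of 3. That may settle 5.3.3 against 5.3.1, but it does not reconcile the two sentences inside 5.3.3. One could also read the last sentence as covering only patients who need a further reduction after level −2, but it does not say so.

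The safety weight can also be pressed too far. One branch stops the drug. The other gives a reduced dose, with investigator discretion under 6.2 and committee review under 12.1. This stands, and it limits the consequence without removing the contradiction.

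A reader might infer three stronger things that the documents do not support.

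- **That seven weeks was intended in 5.3.2.** The 21-day limit in 6.2 seems to favour three weeks, but it counts drug interruption from an unstated start. Dosing ends on Day 12. Counted from there, 21 days ends on Day 33 (12 + 21), near five weeks. A restart seven weeks after the prior cycle start would follow 49 − 12 = 37 drug-free days. A restart at five weeks would follow 35 − 12 = 23, so 6.2 does not match the gloss exactly either. The documents show that the two figures disagree, not which is wrong.
- **That there is no stopping point.** The table ends at 25 mg/m² and 6.2 lets the investigator stop. The limit of 3 is unusable, but exposure is not open-ended.
- **That level −2 should go if only one reduction is meant.** The two-reduction stop stands in the hematologic section. Deleting the level would also take 25 mg/m² away from patients with non-hematologic toxicity, whom 5.3.2 does not restrict.

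**Conclusion.** All three conflicts are present in the current text. For the hematologic events listed in 5.3.3, a recurrence leads both to 25 mg/m² and to removal. The limit of 3 reductions in 5.3.1 exceeds the two reduced levels that exist. The 3-week delay in 5.3.2 and its five-week gloss are 14 days apart on 28-day cycles.

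The first conflict matters most, because it gives opposite orders after a severe toxicity. The other two are wording errors in operative rules.

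Few patients are likely to be affected: about 1 to 2.5 of 30 with a first event on the assumptions in Step 5, and fewer with a recurrence. This takes the 5.3.3 triggers as printed, where both neutropenia triggers involve fever. If prolonged neutropenia without fever was meant, the number is higher and the documents give no rate for it. The only bound is loose: 9.1.7 reports Grade 3-4 neutropenia in 38%, and 0.38 × 30 = 11.4 first events of any duration.

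Sample size and error rates do not change, since 11.1 builds them on the response rate and the 14- and 30-patient stages.

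**What to change.** 1. **5.3.1 and 5.3.3.** State one maximum that fits the table in both places: discontinue TAS-102 if more than two dose reductions are required. This replaces the limit of 3 and the last sentence of 5.3.3, and the recurrence sentence then works as written.
2. **If only one reduction is intended for hematologic toxicity.** Delete the recurrence sentence in 5.3.3, keep the last sentence, and keep level −2 for non-hematologic toxicity. The limit in 5.3.1 still has to come down to two.
3. **5.3.2.** Make the limit and its gloss agree. If the 3-week delay in cycle start stands, the gloss must read seven weeks. If five weeks was meant, the delay must read 1 week. The sponsor has to say which.
4. **6.2.** State the date from which the 21 days of interruption are counted.

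The cost is a short text amendment to 5.3.1, 5.3.2 and 5.3.3 and a clause in 6.2. No extra patients, visits or procedures are needed.
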